5.5.1. Primary outcome

The primary outcome of interest is conversion to psychotic disorder by 24 month follow up (definition in 5.4).

5.5.2. Secondary outcomes

Secondary outcomes of interest are: remission, recovery and relapse of CHR status, psychosocial functioning, persistent and incident non-psychotic disorders, and persistent negative symptoms.

6. Study Design

6.1. Description

This is a non-interventional study examining clinical trajectories and predictors of outcomes in the CHR clinical population. The CHR cohort will be followed over a 24-month period and will receive study assessments at regular intervals. CHR participants will receive ‘treatment as usual’ (i.e., treatment will not be controlled). The HC cohort will be assessed at baseline. A subset of the HC cohort will receive repeat assessments at 2-month follow up.

6.2. Study Setting

The study will recruit across the following sites:

1. Melbourne - Orygen Specialist Programs, Melbourne
2. Melbourne - headspace Glenroy
3. Melbourne - headspace Werribee
4. Melbourne - headspace Sunshine
5. Melbourne - headspace Craigieburn
6. Melbourne - headspace Melton
7. Melbourne Orygen Clinical Trials Unit, Parkville

8. Adelaide – headspace Adelaide and Adelaide HEP (headspace Early Psychosis program)
9. Gwangju Early Treatment & Intervention Team (GETIT) Clinic, Gwangju, South Korea
10. Early Psychosis Intervention Programme (EPIP) Clinic, Buangkok, Singapore
11. Academic Medical Centre (AMC), Amsterdam, The Netherlands
12. Copenhagen Research Center for Mental Health (CORE), Copenhagen, Denmark
13. The University Hospital Jena, Department of Psychiatry, Jena, Germany
14. University of Cologne, represented by the University Hospital of Cologne (UHC), Cologne, Germany
15. Treatment and Early Intervention in Psychosis Program (TIPP) & Center for Psychiatric Neuroscience (CNP), Department of Psychiatry, Lausanne University Hospital, Lausanne, Switzerland
16. Forward Thinking Birmingham, Birmingham, UK
17. Department of Psychiatry, University of Hong Kong

The non-Australian CHR sites have been selected on the basis of proven capacity to recruit CHR participants, previous collaborations with the coordinating centre, high-quality assessment practices, and expertise with the proposed assessment battery.

6.3.Cohort

CHR: 937 CHR patients as determined using standardised PSYCHS diagnostic criteria (see 7.4).

Healthy control (HC) participants: 250 healthy controls will be recruited from the community.

6.4.Methodology and Design

Participants from both samples will be assessed at Baseline. Refer to Section 8.0 for a full list of the measures and their explanation. The CHR sample will be followed up at regular intervals (see 8.0) for a total period of two years. A two year follow up period has been found to capture most CHR cases who convert to psychotic disorder⁹¹. Contact will be made with CHR participants between assessment time points (via phone calls, text messages or emails) in order to maintain engagement and address any technological troubleshooting issues with the digital momentary assessments. It is intended that if CHR participants are unable to be re-interviewed, their diagnostic status at last clinical contact will be sourced from their medical record files and state medical records (the client management interface [CMI] database for Victoria, Australia or local equivalent). HC participants will be assessed at baseline, at 2-month follow up, and at 12-month and 24-month follow up (see section 8.0).

The **screening visit** will take approximately 2 hours to complete. The **full baseline assessments** will take approximately 9–10 hours to complete (3-4 hours for clinical assessments, 1 hour for neurocognitive assessment, 2 hours for neurophysiological

assessments, 1.5 hours for neuroimaging, 20 minutes for free speech recording, and 30 minutes for blood). A saliva sample will be also be collected during one of the baseline visits. The baseline assessments may be completed over multiple sessions in order to minimise participant fatigue. There will also be a 30-min induction/information session at baseline for the digital momentary assessment component. The approximate duration of **follow up assessments** are as follows:

- **Months 1 and 3:** (90 minutes for clinical assessment)
- **Months 2:** 7.5 -8.5 (2-3 hours for clinical assessment, 45 minutes for neurocognitive assessment, 2 hours for neurophysiological assessment, 20 minutes for free speech recording, 30 minutes for blood, and 1.5 hours for neuroimaging)
- **Months 4, 5, 7, 8, 9, 10 and 11:** 20 minutes (BPRS clinical assessment only)
- **Month 6:** 2.5 hours (2 hours for clinical assessment and 30 minutes for neurocognitive assessment)
- **Month 12:** 3.5-4 hours (2.5-3 hours for clinical assessment, and 30 minutes for neurocognitive assessment)
- **Month 18:** 2 hours (clinical assessment)
- **Month 24:** 3.5 hours (2.5-3 hours for clinical assessment and 45 minutes for neurocognitive assessment)

As an acknowledgement of the time and effort involved in taking part in the study, participants will be reimbursed as outlined below:

- \$60 for the baseline clinical interview
- \$40 for each follow up clinical assessment time-point
- \$40 for each neurocognitive assessment
- \$50 for each MRI
- \$50 for each EEG assessment
- \$30 for each free speech interview
- \$30 for each blood test
- \$30 for a saliva sample time-point which includes 3x samples over 2 hours
- Up to \$150 (depending on how much the participant completes) for the digital assessment component. This will be paid pro rata in monthly instalments.

In order to acknowledge the contributions of participants who complete all assessment components and time points as part of the study (excluding the digital assessment component), a 'completion payment' of \$100 (\$50 for healthy controls not selected for the 2-month follow up) will also be provided to the participant at the end of the study along with their month 24 follow up clinical assessment payment.

7. Participant Population

7.1. Description

CHR patients and HC patients aged between 12-30 (inclusive). For further information about study group criteria refer to Section 7.4.

7.2. Sample Size and Power

The size of the CHR sample is primarily determined by the aim of developing a prediction model for conversion to psychosis by 24 months (the primary outcome of interest). This will be achieved by combining data from the PRESCIENT and ProNET networks (i.e., the AMP SCZ dataset as whole), given that the protocols and schedule of assessments have been harmonised across the two networks. The projected CHR sample size for PRESCIENT is 937 and for ProNET 1,040 (combined n of 1,977). There is no uniform method for determining an adequate sample size for developing a prediction model⁹². In this sample size calculation, the method recently described by Riley et al⁹³ was used. Minimum sample size calculations required for various scenarios are provided in table 1. below. Specifically, the sample sizes were derived for the scenarios of having low, medium or high prediction performance and also for the number of parameters in the model being 10, 20, 30, 40 or 50. Conversion to psychosis is a time-to-event outcome and therefore a survival model such as Cox regression is appropriate. The table below shows the sample sizes for the survival outcome, assuming a conversion rate of 15% over 2 years (number of events=300).

Table 1. Minimum sample sizes for survival outcome.

		Number of parameters in model				
		10	20	30	40	50
Predictive performance	low	422	843	1265	1686	2108
	medium	398	796	1193	1591	1989
	high	366	732	1098	1464	1830

It is undesirable to have the number of parameters above 30 as this would result in a prediction model that is overly cumbersome in real-world settings. As indicated in the table, the minimum sample size for a model with 30 parameters is estimated to be between 1100 and 1300. However, as in all medical research, larger sample sizes lead to more robust models and it would therefore be desirable to achieve a sample size larger than this minimum recommendation. Therefore, we aim to assemble as large a sample as possible given the constraints of the length of the recruitment period and the number of recruitment sites. The sample size calculations presented in the table indicate that the overall AMP SCZ sample size of 1,977 is adequate for developing a prediction model with ~30 parameters that has high predictive performance, while still allowing a subset of the data to be 'held back' for external validation purposes (see section 14).

In addition, a simulation analysis was performed testing the performance of a linear kernel support-vector machine (SVM) to separate an event sample (converted cases) from a non-event population (non-converted cases) using 5-fold cross-validation. Results indicated

that with the proposed sample, SVM produces a favourable BAC>70% for an event rate of >0.2 and 10% moderately predictive features in a data space of up to 5000 features.

The size of the HC sample was determined primarily to control for site effects, particularly for neuroimaging data. Based on simulation analyses in the PRONIA study dataset⁶⁴, 15 HC per MRI scanner is recommended to control for site effects. 11 MRI scanners will be used across the recruitment network (Melbourne sites 1–7 will use the same scanner). Therefore, the 250 HCs to be recruited across the PRESCIENT network is sufficient. A subset of these HC participants (70 in total: 20 from Melbourne, 5 from each of the other sites) will receive 2 month follow up assessments in order to model stability of biomarkers. A larger HC sample will be recruited at the Melbourne hub (n=100) compared to other PRESCIENT sites (n=15 per site) because a larger sample of CHR participants will be recruited in Melbourne compared to other sites and, therefore, a larger HC sample is required at that site in order to accurately match HC to CHR on relevant variables (see 7.4).

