8.2. Demographics, Medical and Psychiatric History

Demographic information (age, sex, gender, race, ethnicity, socioeconomic status, employment, educational attainment and age and education of biological parents) and medical and psychiatric history will be collected. Prior treatment (pharmacological and psychosocial treatment and health service utilisation) will also be captured, based on information collected from the participant and, as required, medical files, family and/or pharmacist.

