8.7. Neurophysiological Assessments (EEG Recordings)

EEG will be acquired during 4 paradigms:

1. **Mismatch Negativity (MMN)/Visual Oddball Paradigm.** The participant performs a visual oddball target detection task while ignoring the auditory tone stimuli presented.
 - a. MMN Paradigm: Measures include
 - i. Mismatch Negativity (MMN) amplitude - Pitch+Duration “Double Deviant tones”.
 - ii. Repetition Positivity (RP) amplitude - difference between late and early appearing standards within a local series of standards in MMN paradigm.
 - b. Visual Oddball Paradigm: Measures include
 - i. Visual Target P300 (P3b) amplitude
 - ii. Visual Novelty P300 (P3a) amplitude
2. **Auditory Oddball Paradigm:** Measures include
 - a. Auditory Target P300 (P3b) amplitude
 - b. Auditory Novelty P300 (P3a) amplitude

- c. Auditory Target and Novel Alpha Desynchronization
3. **40 Hz Auditory Steady State Response:** Measures include
 - a. 40 Hz Inter-trial Phase Coherence (ITC)
 - b. Baseline inter-stimulus interval Gamma Power
4. **Resting state EEG (eyes open/eyes closed):** Measures include
 - a. Power spectra: delta, theta, alpha, beta, gamma
 - b. 1/f slope: Thought to reflect excitation/inhibition balance.

Frequency: EEG data will be acquired at baseline and at 2 month follow up. The protocol for baseline and follow up is identical. The purpose of the follow up assessment is to assess change trajectories predictive of CHR outcomes. Each EEG session will require between 90 minutes and 2 hours from set-up to clean-up.

Instruments: Identical 64-channel ActiChamp High Impedance EEG systems and an air-gapped acquisition computer and stimulus presentation device will be leased from a private vendor (NeuroSig) and installed at all sites.

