Following the completion of analyses for the study, the remaining blood samples will be shipped to the NIMH Repository and Genomics Resource (NRGR). Samples will be stored in the repository indefinitely and made available to other researchers upon application for future research purposes.

At baseline and month 2, saliva samples will be collected to measure cortisol levels, indicative of stress response. At both baseline and month 2, two vials will be collected at time 1, two vials at time 2 (1 hour later), and two vials at time 3 (two hours from time 1). All saliva samples will be shipped to NRGR. NRGR will then ship 1 vial per time point (i.e., 3 baseline vials and 3 month 2 vials) for each participant to a to be determined commercial lab such as Salimetrics in the US for analysis and store the remaining samples for future research.

Additionally, data from the FIGS (family history of psychiatric disorder) may be used to inform genetic analyses; recorded history of health conditions may inform biomarker analysis; vital signs, current illness and recent physical activity will be captured as they may confound biomarker measurement.

The type of genetic analysis being conducted in this study is not expected to result in information about individual participants' future health, future treatment or risk of having children with a genetic disorder, or information that may be relevant to the health of family members who are not part of the project.

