Of the existing prediction models in the field, the one that shows the strongest performance in the PRESCIENT sample may be made into an online risk calculator for preliminary use in some clinical settings (e.g., to allow clinical decision-making regarding the value of further assessments, such as referral for imaging), as in other areas of medicine^{e.g.121}, and to allow stratification for aetiological and treatment research. Importantly, because the PRESCIENT dataset will include participants recruited from both primary and specialist service settings (*headspace* and HEPs/Orygen), the risk calculator will be able to be calibrated for type of recruitment/service setting, which has been found to be an important factor in risk prediction in this field¹²². This use of the PRESCIENT dataset to externally validate existing and forthcoming prediction models will address one of the key limitations in the field⁹, namely the lack of robust validation procedures on prediction models.

Developing new prediction models (specific aim 2c)

Critically, the PRESCIENT dataset will facilitate the development of new, more refined prediction models, and associated risk calculators, that take advances in the field into account (such as iterative and dynamic prediction, see 2.3) and which directly address the limitations identified in the field (lack of internal and external validation; low ratio of converted cases to number of predictor variables; lack of pre-selection of predictor variables; inappropriate methods of presenting model performance; not covarying for treatment received; insufficient use of clinical

comparison groups^{9, 123, 124}). Data from the PRESCIENT and ProNET networks will be combined (i.e., the AMP SCZ dataset) for the development of these new prediction models. The primary purpose of these new prediction models will be to guide stratification of patients in future pharmacological clinical trials, in line with the overarching aim of AMP SCZ to develop new treatments for the CHR stage of illness.

There are a number of reasons that the AMP SCZ dataset will be able to *improve* on prediction models based on existing datasets and which may be far more useful for treatment decision-making and treatment development:

1. *Scale and multimodal data*: The size of the dataset (approximate CHR n of 2000) and the comprehensive suite of multimodal data will provide greater predictive accuracy in model development and allow the integration of multiple data types.

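### Section 7.2 judges 1,977 adequate by the size of the finished model (~30 parameters), but Section 14 selects that model from a larger, uncapped candidate pool, so adequacy with data held back is not shown

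*Protocol*

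**What the plan says.** Protocol Section 7.2 bases the CHR sample mainly on developing a model for conversion to psychosis by 24 months, using PRESCIENT and ProNET together (937 + 1,040 = 1,977). Table 1 gives minimum sample sizes for a survival model with 10 to 50 parameters, in rows labelled low, medium and high predictive performance.

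The section prefers no more than 30 parameters because a larger count would give "a prediction model that is overly cumbersome in real-world settings". It reads the table at that count: "As indicated in the table, the minimum sample size for a model with 30 parameters is estimated to be between 1100 and 1300". It then says that "1,977 is adequate for developing a prediction model with ~30 parameters that has high predictive performance", with a subset still available to hold back for external validation. No share is given for that subset.

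Section 14 describes how the model is obtained. LASSO and stepwise selection choose the predictors. The candidates include the range of assessments in 8.1, and their number is described as high. Data reduction is permitted but not required, and no target number is set. Section 14 gives a concordance index of at least 0.7 as its mark of good performance.

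**The concern.** The two sections count different things. Section 7.2 counts the terms that remain in the finished model. How far a selected regression model overfits depends on how many candidate parameters were searched, not on how many survived. A 30-term model chosen from 60 candidates does not have the sample-size requirement of one fitted to 30 terms named in advance.

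Section 7.2 is not consistent on this. Its next paragraph sizes the support-vector machine by inputs: "10% moderately predictive features in a data space of up to 5000 features". Section 14 names "lack of pre-selection of predictor variables" and a low ratio of converted cases to predictors among the field's limitations it will address, yet fixes no pre-selection beyond the choice of instruments.

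At stake is the stated justification of the sample for the primary outcome. Development and hold-out draw on the same 1,977 people, so each candidate beyond 30 uses up part of what 7.2 treats as available for validation.

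A second, smaller gap is that no R², c-index or shrinkage value is attached to low, medium or high. The rows cannot be compared with Section 14's mark of 0.7.

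**Working it through.** **1. Reproduce Table 1 at 30 parameters.** The table is linear in the number of parameters. From the 50-parameter column, participants per parameter are:
- low: 2108/50 = 42.16
- medium: 1989/50 = 39.78
- high: 1830/50 = 36.60

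Multiplying by 30 gives 1,265, 1,193 and 1,098, which are the table's entries and match the rounded 1100 to 1300 in the text. Subtracting from 1,977 leaves 712, 784 and 879. So at 30 parameters the sentence agrees with the table.

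**2. Candidates that 1,977 supports.** With share h held back, the maximum is (1 − h) × 1,977 / k, where k is participants per parameter. At h = 0:
- low: 1977/42.16 = 46.9, so 46
- medium: 1977/39.78 = 49.7, so 49
- high: 1977/36.60 = 54.0, so 54

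**3. A count of 8.1 (my count, not a protocol figure).** Measure rows for CHR participants, leaving out consent, eligibility and adverse events: clinical 17, digital 2, neurocognition 11, EEG 4, biospecimens 7, speech and face 4, MRI 1, treatment 1. The total is 47. Leaving out vital signs, current health status and blood count gives 44. Section 8.8 describes these as possible confounders: "vital signs, current illness and recent physical activity will be captured as they may confound biomarker measurement", and white cells are measured for the same reason.

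**4. What those counts need.** Need = candidates × k; left = 1,977 − need.

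| Candidates | Low | Medium | High |
|---|---|---|---|
| 44: need | 1,855 | 1,750 | 1,610 |
| 44: left | 122 (6.2%) | 227 (11.5%) | 367 (18.5%) |
| 47: need | 1,982 | 1,870 | 1,720 |
| 47: left | none | 107 (5.4%) | 257 (13.0%) |

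**5. Rows hold more than one variable.** The demographics row covers "age, sex, gender, race, ethnicity, socioeconomic status, employment, educational attainment" and more (Section 8.2), and the functioning row covers three scales. Take EEG alone. Section 8.7 lists 4 measures for the mismatch negativity and visual oddball paradigm, 3 for the auditory oddball, 2 for the 40 Hz response, and 6 at rest ("Power spectra: delta, theta, alpha, beta, gamma" plus the 1/f slope). That is 15 measures in 4 rows, which adds 11 candidates: 44 + 11 = 55 and 47 + 11 = 58.
- 55 candidates need 2,319 / 2,188 / 2,013 (low / medium / high).
- 58 candidates need 2,445 / 2,307 / 2,123.

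All six figures exceed 1,977 before anything is held back.

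**The case against.** Several points on the other side stand.

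- At 30 parameters Table 1 supports the sentence, so this is not a calculation error.
- The sentence refers to high performance and an unspecified subset. In the high row, 44 to 47 candidates still leave 13-19%, which is a subset.
- The count of 44 to 47 is a judgement, and rows are not parameters. Section 14 does not say that one Cox model receives every row. Section 5.3.3 describes comparing combinations of modalities, and the digital component is optional.
- Data reduction could bring the candidates down to 30, and LASSO's penalty gives some protection.
- Section 7.2 aims for as large a sample as recruitment allows, so the table did not fix 1,977.
- Bootstrap validation and the held-back sites would reveal overfitting.

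It can also be said that the candidate list, the reduction rule and the hold-out share are SAP matters, and Section 14 calls itself a broad outline. That is fair for the list and the share. But 7.2 draws a conclusion now, and the analysis outlined in the same document does not support it. Detecting overfitting later does not make the development sample sufficient, and stepwise selection lacks LASSO's penalty.

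A reader might try to work back from Table 1 to the performance each row assumes, and infer that even the low row is optimistic beside the 0.7 mark. The documents do not support that. They state no criterion or shrinkage target, and the answer falls on either side of 1,977 depending on what is assumed.

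**Conclusion.** The point holds: the adequacy of 1,977 with data held back is not demonstrated for the analysis that Section 14 describes. The reading at 30 carries over only if about 30 candidates enter selection, and neither section says so. By Table 1 the ceiling is about 46, 49 or 54 candidates with nothing held back. At 44 rows the remainder is 6-19% across the three table rows, and at 47 rows it is 0-13%. Splitting only the EEG rows passes the ceiling in all three.

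This rests on Table 1's linear rates, on counting candidates rather than survivors, and on my row count. A reader might infer that 1,977 is too small. The documents do not support that, because reducing the candidates in advance to about 30 would restore the conclusion of 7.2. The undefined rows are a separate gap in reporting: the sample sizes cannot be related to Section 14's benchmark.

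**What to change.** 1. In Section 7.2, define parameters as candidate parameters entering selection. Replace the adequacy sentence with what Table 1 supports: about 46, 49 or 54 candidates (low, medium, high) with no data held back, falling in proportion to the share of participants held back.
2. For each row of Table 1, state the performance value (R² or c-index) and the criterion that produced the sample sizes, including any shrinkage target.
3. In Section 14, for the regression models, turn the optional data reduction into a requirement: reduce the candidates, without reference to outcome, to no more than the number stated in 7.2.

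The cost is an annotated table and a few reworded sentences, with no added participants. The downside is a less favourable stated parameter count.
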